2. STUDY DESIGN

2.1 Design

EARNEST is a multicentre, open label, superiority RCT, allocating consenting patients with uTBAD in the sub-acute phase in a 1:1 ratio to TEVAR and BMT and surveillance (TEVAR+BMT+SURV) or BMT and surveillance (BMT+SURV). It will have adjudicated endpoints and an internal pilot. Each patient will be followed up for a minimum of 5-years.

Patients with uTBAD in the sub-acute phase (from 10 days to 3 months after the aortic dissection occurs) will be identified at vascular centres and regional network hospitals. After consent, participants will be allocated in a 1:1 ratio to TEVAR and BMT (TEVAR+SURV+BMT) or BMT and surveillance (BMT+SURV) using a using a minimisation algorithm, incorporating a random element, to ensure groups are well balanced for centre, age and sex. We refer to this as randomisation.

Those in the TEVAR+BMT+SURV group will undergo the intervention, TEVAR, at 25 specialist vascular sites in the UK. To ensure the highest standards of care and consistency across all participating centres in the clinical trial of Thoracic Endovascular Aortic Repair (TEVAR) for Type B Aortic Dissection (TBAD), a credentialing process will be implemented. This process will assess each centre's capability, infrastructure, and experience in performing TEVAR for uTBAD, ensuring compliance with established guidelines and standards.

Criteria for Credentialing for Participating Centres:

- 1. Multidisciplinary Team (MDT) and compliance with standard procedures:
- Centres must have an established MDT experienced in managing TBAD cases, including vascular surgeons, interventional radiologists, cardiologists, and specialist nurses.
- The MDT must demonstrate compliance with the "Provision of Vascular Services" document distributed by the Vascular Society of Great Britain and Ireland (2021).
- 2. Infrastructure and Facilities:

Confidential Page 19 of 30

EARNEST	Protocol No:	Sponsor:	Imperial	College	V1.0 7 th Oct 2024
	174766	London	por.u.	ooogo	

- Centres must provide comprehensive details of the unit's infrastructure and available facilities for the treatment of TBAD patients, including endovascular suites, post-operative care facilities, and availability of advanced imaging technologies.
- 3. Standard Operating Procedures (SOPs) and Service Provision:
- Centres must submit their SOPs and detailed documentation of their uTBAD patient care pathways, including pre-operative, intra-operative, and post-operative management protocols.

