4.3 Randomisation and Blinding

Randomisation: 470 participants will be allocated to treatment group (1:1) by minimisation, which assigns the next patient to the group that balances the main prognostic factors (e.g., age, sex, centre) with high probability (e.g., 75%). This will be generated by computer algorithm and released after checking patient eligibility and written consent. This will be implemented by a validated web-based system Sealed Envelope. Once a participant is confirmed to be eligible for randomisation, qualified site staff will register the participant on the system and randomise them. A participant ID will be generated which must be used to identify participants on CRFs from this point.

Blinding: For ethical and practical reasons, participants and clinicians cannot be blinded to treatment allocation. However, endpoints will be adjudicated by an expert panel (PROBE study - Prospective Randomized Open, Blinded End-point).[18]

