7.2 Planned recruitment rate

We estimate a single centre to open for the first 4 months, then recruit one centre a month until there are 25 (over 28 months). When open, the average recruitment per centre per month will be 0.7 participants.

At 18 months we expect 15 centres open, and 86 participants randomised. At the end of the internal pilot phase (at 18-months), the number of sites open to recruitment, recruitment rates and adherence to allocated treatments will be assessed

Red, amber and green outcomes will be set for recruitment, site opening and data completion. The outcome will be judged as RED if centres have recruited less than 30 participants which equates to less than 35% of the projected numbers at this stage; AMBER if centres have recruited 30-85 participants which equate to 35- 100% of the projected numbers at this stage; and GREEN if centres have recruited over 86 participants which equate to >100% of the projected numbers at this stage. At the end of the internal pilot the number of centres actively recruiting; data completion and visit completion at 6-weeks will be assessed in the same way.

Progression Criteria	Red	Amber	Green
Number recruited	<30 participants	30-86 participants	>86 participants
Number of sites opened	<5	5-15	>15
Data completion	<70%	70-85%	>85%
6-week clinical follow up completed	<70%	70-85%	>85%

Table 1: Progression criteria after 18 months of recruitment to the EARNEST trial generated using the internal pilot.

Predicted recruitment is 470 participants in the UK over 42-months, an average of 135 patients/year (we estimate this will be 1 in 4 patients with acute uTBAD presenting to sites).

Confidential Page 34 of 30

EARNEST	Protocol No:	Spansari	Imperial	Collogo	V1.0 7 th Oct 2024
EARNEST	174766	Sponsor: London	imperiai	College	V1.0 7 OCI 2024

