7.3 Statistical Analysis

Statistical analysis is the responsibility of [name] at LSHTM. The analysis and reporting will conform to the standards set by the Consolidated Standards of Reporting Trials statement.[22] Analysis will be undertaken guided by a pre-specified Statistical Analysis Plan (SAP), which will be approved by the TSC, prior to database lock. Any deviations from the SAP will be justified and documented in the final report.

(i) Analysis populations

Primary statistical analysis will be based on the intention to treat principle. Participants will remain in the study from randomisation to end of follow up and be analysed in the group to which they were randomised. This primary analysis will take place when all participants are at least 5 years post-randomisation.

An interim analysis will take place at one year after randomisation to report the outcomes of the TEVAR procedure (complication rates and early outcomes). There will be no formal assessment of the need to stop the trial on the basis of efficacy at this stage. No other interim analyses for efficacy will be undertaken.

(i) Primary Endpoint Analysis

An independent outcome adjudication committee working to strict protocols will review all reported primary endpoints using source data.

Times from randomisation to the first primary outcome component will be summarised using Kaplan-Meier estimates. Participants who do not have an event or are lost to follow up (including due to intercurrent events such as non-aortic death) will be censored at last visit. This has been termed the Hypothetical Strategy estimand, since it assumes that people who are censored would have had the same risk as those who are not censored, if they had remained in the study. The estimand for our primary analysis is the hazard ratio for the comparison between TEVAR and BMT, estimated from a Cox proportional hazards model (after checking the model assumptions) adjusting for minimisation variables age and sex as fixed effects and centres as random intercepts. The treatment hazard ratio, 95% confidence interval and Wald p-value will be reported.

(ii) Secondary Endpoints Analysis

- Similar survival model methods will be used for secondary time to event outcomes, including aortic-related mortality, all-cause mortality and reinterventions.

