- The number of complications each participant experiences will be analysed using negative binomial models, with patient as the random effect, treatment arm and the minimisation factors as fixed effects and adjusting for time at risk.
- Rate of aortic remodelling between TEVAR+BMT+SURV and BMT+SURV groups will be analysed by the core lab. CT angiograms at presentation of the index event, six weeks post TEVAR/or after dissection and one year will be analysed by the core lab according to a standard protocol. The rate of false lumen thrombosis and

Confidential Page 35 of 30

EARNEST	Protocol No: 174766	Sponsor: London	Imperial	College	V1.0 7 th Oct 2024

maximum diameter/area of false lumen, true lumen and whole aorta as well as ratios will be compared between groups.

 Patient reported outcomes measured over time, including the index value from the EQ-5D-5L, will be analysed using linear mixed models. We will first decide on the most appropriate covariance structure. This means starting with a saturated mean model (including treatment, age, sex, baseline index value and all interactions) and exploring patient-specific random intercepts, random slopes and their correlations. After fixing this covariance structure, we force treatment, age and sex into the model, assuming a constant treatment effect over time. This again reflects a hypothetical strategy estimand for the treatment effects at each time point.

(iii) Safety

All Serious adverse events will be reported by treatment arm, stratified by severity, relationship to treatment/trial conduct whether or not they are expected. Statistical monitoring of safety data by ICTU will be conducted throughout the trial and reported at agreed intervals to the DMEC.

(iv) Exploratory analysis

- We will explore the relationship between initial aortic diameter and changes over time through estimation of the correlation between random intercepts and random slopes (covariance structure).
- We will explore the effects of other baseline measurements and CT criteria and their interactions with treatment arm, on long-term aortic growth.
- Further exploratory analysis may be undertaken should it be warranted.

(v) Sensitivity Analysis

For technical details of the following sensitivity analysis, see the SAP.

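### The EQ-5D-5L model in section 7.3(ii) leaves out centre, a minimisation factor, so its standard error may be slightly too large

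*Protocol*

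**What the plan says.** Protocol section 2.1 has participants allocated 1:1 by minimisation with a random element, "to ensure groups are well balanced for centre, age and sex". Section 4.3 names the same three factors and gives 75% as an example of the probability of assigning the balancing arm.

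Section 7.3 then specifies the models:

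- **Primary Cox model:** "adjusting for minimisation variables age and sex as fixed effects and centres as random intercepts". Secondary time-to-event outcomes are to use similar methods.
- **Number of complications:** a negative binomial model with "treatment arm and the minimisation factors as fixed effects".
- **EQ-5D-5L index over time:** a linear mixed model built in steps. The covariance structure is chosen first, from a full mean model in treatment, age, sex and baseline index value with their interactions. The candidate random effects are at patient level only: "exploring patient-specific random intercepts, random slopes and their correlations". The mean model is settled in the last step, which reads: "After fixing this covariance structure, we force treatment, age and sex into the model". The treatment effect is taken as constant over time.

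The terms of the EQ-5D-5L model are therefore given in three lists: starting mean terms, candidate random effects and forced terms. Age and sex appear among the mean and forced terms. Centre appears in none of the three.

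**The concern.** When allocation is balanced on a factor that predicts the outcome, the two arms have nearly the same mix of that factor, and the treatment difference varies less than it would under simple randomisation. The model recovers this gain only if it contains the factor. If the factor is left out, its variation goes into the between-patient variance, and the reported standard error describes an unbalanced design that was not used. The interval is then too wide and the test rejects too seldom.

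For quality of life, a named secondary objective, the protocol includes two of the three balancing factors and not the third, and gives no reason. What is at stake is a little precision and agreement between the quality-of-life model and the protocol's other models.

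**Working it through.** **The plan's own figures.** The protocol gives no standard deviation, target difference, power or centre ICC for EQ-5D-5L, so there is no figure on this point to reproduce. The sample size, used below as n, does reproduce. Events = (1.96 + 1.2816)² / (0.25 × (ln 0.4)²) = 50.06, rounded up to 51; 50.06 / 0.1197 gives 419 patients; 419 / 0.9 gives 466, against the stated 470. The point is about model specification, not arithmetic.

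**Inputs from the protocol.**

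- 470 patients in 25 centres (sections 7.1 and 7.2), on average 470 / 25 = 18.8 per centre.
- One centre for the first 4 months, then one more each month up to 25, with 42 months of recruitment at 0.7 per centre per month (section 7.2). Taking openings at month 0 and at months 4 to 27 gives 678 centre-months, and 678 × 0.7 = 474.6, close to 470. Expected centre sizes run from 15 × 0.7 = 10.5 to 42 × 0.7 = 29.4.
- Minimisation on centre, age and sex, favouring the balancing arm with probability 0.75 (sections 2.1 and 4.3).

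**Assumptions not in the protocol.** Centre ICC ρ of 0 to 0.10; three equal age bands; 35% in one sex group. The outcome is each patient's mean over visits, which is the between-patient part of a mixed model with a constant treatment effect. Baseline index value is not in the model.

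**Method.** 3,000 allocations were simulated. Let X hold the intercept, treatment, age bands and sex (5 columns), D the centre indicators, L the treatment row of (X′X)⁻¹X′, and M the residual projection of X. With total variance 1, for each allocation:

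- true variance of the estimate without centre = ρ‖LD‖² + (1 − ρ)‖L‖²;
- reported variance without centre = s² × [(X′X)⁻¹] for treatment, where s² = {ρ tr(D′MD) + (1 − ρ)(n − 5)} / (n − 5);
- variance with a centre random intercept, from generalised least squares.

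Variances were averaged over allocations. With r = reported SE / true SE, the actual two-sided type I error is 2 × {1 − Φ(1.96 r)}.

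| Centre ICC | Reported SE / true SE | Actual type I error | SE without centre / SE with centre random intercept |
|---|---|---|---|
| 0 | 1.000 | 5.0% | 1.000 |
| 0.01 | 1.004 | 4.9% | 1.004 |
| 0.02 | 1.007 | 4.8% | 1.008 |
| 0.05 | 1.019 | 4.6% | 1.022 |
| 0.10 | 1.039 | 4.2% | 1.047 |

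Example at 0.10: 1.96 × 1.0388 = 2.036, and 2 × {1 − Φ(2.036)} = 0.042.

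**Control.** With simple randomisation in place of minimisation, reported SE / true SE is 1.000 at every ICC. The excess therefore comes from balancing on centre and then omitting it.

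**Precision of the check.** Simulating outcomes directly, with 3,000 runs per ICC, gave ratios scattered between 0.980 and 1.032. The simulation error of such a ratio is about 1/√6000 = 1.3%, too coarse for effects of this size. The table therefore uses variances calculated exactly for each allocation.

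**Effect on power, for scale only.** Take a comparison that would have 90% power at the true SE. Power is Φ(3.2415 − 1.96 r): 89.9% at ICC 0.01, 89.3% at 0.05 and 88.6% at 0.10. The 90% is a benchmark; the protocol sets no power for EQ-5D-5L.

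**The case against.** The strongest objection is that this belongs to the statistical analysis plan. Section 7.3 refers to a separate plan, and forcing terms into a model sets a minimum that does not bar others. A reader might infer that the protocol has decided to exclude centre. The text does not say so, and the analysis plan could add it. What remains is that the protocol does not defer this model: it names the mean terms, the random effects and the forced terms. An analyst who followed those lists would fit a model without centre.

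Three stronger readings are also tempting, and the documents do not support them.

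- *That the standard error is certainly too large.* That needs EQ-5D-5L to vary between centres. The protocol gives no ICC, and at zero there is no excess.
- *That the inflation is 1/√(1 − ρ)*, which would be 0.5%, 2.6% and 5.4% at ICC 0.01, 0.05 and 0.10. That formula assumes near-exact balance within every centre. A 75% assignment probability shared over three factors, with about 19 patients per centre, does not achieve it.
- *That the protocol breaks a rule of its own.* It sets no single rule: centre is random in the Cox model, while the complications model takes the minimisation factors as fixed. The comparison shows an unexplained gap and no more.

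It is also true that the baseline index value, if kept, would absorb part of any stable centre difference, that the error is conservative, and that this is a secondary outcome. These points limit the size of the problem but do not remove the omission.

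**Conclusion.** The point holds in a small, conditional form. As written, the EQ-5D-5L model omits a factor on which allocation is balanced. If the outcome varies between centres, the reported standard error exceeds the true one by up to about 4% over the assumed ICC range, and the nominal 5% test runs at no lower than about 4.2%. The treatment estimate is not biased and there is no added risk of a false positive.

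The figures rest on the assumed ICC range, on 75% being the probability actually used (section 4.3 offers it only as an example), and on a model without baseline index value. A probability nearer to 1 would move the excess towards the exact-balance limit; keeping baseline would reduce it. A change of conclusion is unlikely except at the margin. This is a worthwhile tidy-up, not a threat to the trial.

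**What to change.** In section 7.3(ii), extend the sentence on the forced terms with a clause such as: *with centre as a random intercept, in addition to the patient-level random effects*. Carry the same wording into the statistical analysis plan.

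A random intercept matches the primary model and costs nothing if centres do not differ. Fixed effects for 25 centres would be less economical: in the direct simulation they made the model-based standard error about 0.7% larger than omitting centre when the ICC was zero (1 / 0.9929 = 1.007).

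The cost is one clause. Centre is already known for every participant because allocation uses it, so no data, visits or patients are added. Fixing it before outcome data are seen also avoids a later, data-driven choice.

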4.4 Visit Schedule

Visit	0	1	2	3	4	5-9
	Screening	Consent	FOR TEVAR+BMT+ SURV only TEVAR Intervention	Clinical and research assessment	Clinical and research assessment	Clinical and research assessment
TIMEPOINT	Within 3 months of index uTBAD	After the requirement for intensive care or high dependency care has ended, and the patient has not received opiate analgesia for at least 48 hours and from 10 days to 3 months of	10 days-3 months after index uTBAD	FOR BMT+SURV 6 weeks after discharge from hospital admission for the index event c (±14 days) FOR TEVAR+BMT+ SURV	6 months after randomisation (±30 days)	1 year and yearly to 5 years after randomisation. (±30 days)

Confidential Page 24 of 30

EARNEST	Protocol No:	Sponsor:	Imperial	College	V1.0 7 th Oct 2024
	174766	London			

		II.		Į.		
		index uTBAD, noting TEVAR must be performed in 3 months after index event		6 weeks after TEVAR ^c (±14 days)		
Inclusion & exclusion criteria	Х	X				
Informed consent		x				
Demography		X				
Medical history		X		X	x	x
Clinical assessment		x		x	x	x
Clinical details of uTBAD admission		x				
Blood pressure ^a		x	x	x	x	x
CTA aorta		Х		Xp		X
Site report of CT Aorta		X		X		X
Transfer of CT to core lab		X		X (six weeks after discharge from hospital after index event OR six weeks after TEVAR)		X, at 1 and 5 years only
EQ-5D-5L		X		x, measured before imaging results are relayed to the participant	x, measured before imaging results are relayed to the participant	x, measured before imaging results are relayed to the participant
Procedural details			X			
Health resource use, from NHS and personal and social care				x	x	х
Document re- intervention				X	X	x
Document adverse events			X	X	X	х

Confidential Page 25 of 30

EARNEST	Protocol No: 174766	Sponsor: London	Imperial	College	V1.0 7 th Oct 2024

^aStandardised BP measurement: This will be measured using standard protocols. At each visit, three BP recordings will be measured in the sitting position using a validated semi-automated device after at least ten minutes rest. The mean of the second and third readings will be used in analyses. Smoking or vaping will not be permitted for 30 minutes before BP measurement.

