7. STATISTICAL ANALYSES

7.1 Sample Size and power considerations

The samples size has been calculated to be 470 participants (235 in each arm), followed up for 5 years.

Our power calculations were made after reviewing published data and re-analysis of data from the ETTAA national cohort study of patients with thoracic aortic aneurysms.[19] Primary outcome is the composite of aortic-related mortality AND/OR severe permanent neurological deficit AND/OR severe permanent cardiorespiratory failure.

Primary endpoint incidence in the SURV+BMT arm of the study: the estimated aortic-related mortality at 5 years is 14.8% taken from the combined results of one long term RCT, one high quality cohort study, and one propensity matched analysis [10, 20, 21]

Confidential Page 32 of 30

EARNEST	Protocol No: 174766	Sponsor: London	Imperial	College	V1.0 7 th Oct 2024

Because the control group has no intervention, the estimated early (up to 30 days) severe permanent neurological deficit and/or cardiorespiratory failure is assumed to be 0% for the BMT group. These complications were not observed in either of two RCTs or a propensity matched analysis in TEVAR or BMT groups.[9, 20, 21]

Using estimates from the INSTEAD trial, [21] the 5-year risk of surgery/stenting was 26.5% in the BMT group. 78% of these patients would be suitable for a stent, with the other 22% of patients requiring surgery. These later interventions are more likely to be complicated and/or emergency procedures, with late severe permanent neurological deficit/cardiorespiratory failure estimated at 8% for those undergoing stenting and 11.29% for open procedures (based on data from ETTAA and observational data from surgical series.[7, 19] Combining risk of a late intervention, with risk of severe permanent neurological deficit/cardiorespiratory failure after an intervention, we expect non-fatal components of the primary outcome (i.e., patients who do not die within five years) of 2.31%.¹

Adding the 14.8% of patients who die within 5 years, the early 30-day non-fatal event rate of 0%, and the longer term non-fatal serious event of 2.31%, *the estimated 5-year incidence* of the composite primary endpoint is 17.11% in the BMT group.

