- In addition to the above ITT analysis, a per-protocol population (PP) will also be defined, which will include all eligible randomised participants according to the treatment received but will exclude major protocol violations. Results from both the ITT and the PP analyses will be presented.
- In an RCT, we do not expect substantial amounts of missing baseline measurements. Therefore, the primary analysis will include complete cases only. However, analysis of the primary outcome and key secondary outcomes could be repeated after using Chained Equations to impute missing baselines multiple times, with resulting estimates of the treatment effects combined using Rubin's rules. This method will be used if more than 10% of cases have some missing baseline data. The method assumes that the incomplete baselines are Missing at Random conditional on measurements that are observed, an untestable assumption.
- The primary outcome analysis assumed non-informative censoring for those participants who did not have the primary outcome during follow up. We will repeat the analysis using inverse probability of censoring weights to adjust for differences between fully observed and censored survival times.

Confidential Page 36 of 30

EARNEST	Protocol No:	Sponsor:	Imperial	College	V1.0 7 th Oct 2024
	174766	London			

- We will consider sub-distribution hazard ratios for the primary outcome to adjust for competing risks such as death from non-aortic causes.
- Other sensitivity analyses will be completed should the trial data or analysis be deficient in another way.

(vi) Cost effectiveness

Cost-utility analysis will consider NHS and personal social services (PSS) costs including productivity losses due to sick leave. The outcomes will be presented as incremental cost per Quality Adjusted Life Year (QALY) gained.

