8.9 Informed Consent

The consent may only take place once the requirement for intensive care or high dependency care has ended, and the patient has not received opiate analgesia for at least 48 hours.

Consent may be undertaken from 10 days to three months (allowing time for TEVAR to take place if necessary) from the index event.

It will be the investigator's responsibility to obtain written informed consent from the subject after adequate explanation of the aims, methods, anticipated benefits, and potential hazards of the study and before any study procedures are commenced.

Consent will also be obtained for participant's contact details to be shared with the central study team for the purposes of future long-term follow-up and optional dissemination of trial results.

Consent will be obtained for the central study team to access routinely collected healthcare data to confirm whether additional procedures/hospital admissions took place during the follow up period and to obtain long term health outcomes after the study has finished.

The Informed Consent Form will be signed and personally dated by both the subject and the investigator, or a person delegated to do so by the investigator. The subject will be provided with a copy of the signed Subject Information Sheet/Informed Consent Form document. The original Informed Consent Form will be retained with the source documents.

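### The per-protocol analysis in Protocol 7.3(v) groups people by treatment received, so events before stenting leave the TEVAR arm and the comparison leans towards TEVAR

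*Protocol*

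**What the plan says.** **Analysis sets.** Protocol section 7.3 makes ITT primary: participants will "be analysed in the group to which they were randomised". Section 7.3(v), Sensitivity Analysis, adds a per-protocol population "which will include all eligible randomised participants according to the treatment received but will exclude major protocol violations", and "Results from both the ITT and the PP analyses will be presented". The list opens with "For technical details of the following sensitivity analysis, see the SAP". That defers technique; the grouping rule itself is fixed in the protocol.

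**Timing.** The clock starts at randomisation: "Times from randomisation to the first primary outcome component will be summarised using Kaplan-Meier estimates". Section 8.9 states "Consent may be undertaken from 10 days to three months" after the index event, and the visit schedule in 4.4 adds "noting TEVAR must be performed in 3 months after index event". Section 5.3 allows TEVAR not to be given at the participant's request, or because of an adverse event or illness arising after entry.

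**Later repair in controls.** Sections 1.5, 2.1 and 5.2 make clinically indicated later repair part of the control strategy. Section 7.1 expects a good deal of it: "the 5-year risk of surgery/stenting was 26.5% in the BMT group", with 78% of these suitable for a stent.

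**The concern.** Everyone counted as having received TEVAR must have been alive and well enough to reach the procedure. A TEVAR-arm participant who ruptures, dies or has a disabling stroke while waiting has received only medical therapy. Grouping by treatment received therefore takes that event out of the TEVAR group, although the clock was already running. Not receiving TEVAR because of a new adverse event or illness is also related to prognosis and acts in the same direction.

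Section 7.3(v) does not say either whether treatment received means sub-acute TEVAR or any TEVAR. On the wider reading, a control stented years later would be counted as TEVAR from randomisation.

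At stake is the meaning of the supporting result. The trial is sized on 57 events, so moving a few changes the estimate, and a per-protocol hazard ratio more favourable than ITT could be taken as corroboration when it comes from the grouping.

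**Working it through.** **The plan's own figure, for scale.** Schoenfeld events for HR 0.4, 90% power, two-sided 5%: 4 × (1.960 + 1.282)² / (ln 0.4)² = 50.06, so 51. Patients: 50.06 / 0.1197 = 418.2, so 419. With 10% loss: 51 / 0.9 = 56.7, so 57 events; 419 / 0.9 = 465.6, so 466 patients against the stated 470. The event target reproduces.

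**Longest wait.** Consent at day 10 and TEVAR by about day 90 gives 90 − 10 = about 80 days.

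**Expected events before stenting** (TEVAR arm, n = 235, no true effect)

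- From section 7.1: 5-year control risk 17.11%. Cumulative hazard = −ln(1 − 0.1711) = 0.1877.
- Assumed: mean wait of 7 to 45 days, and a hazard in the first 90 days of 1 to 5 times the later hazard. The documents give neither.
- Constant hazard, 30-day mean wait: 0.1877 / 5 = 0.0375 per year; 235 × 0.0375 × 30/365.25 = 0.7 events.
- Fivefold early hazard, 45-day mean wait: later hazard = 0.1877 / (5 × 0.2464 + 4.7536) = 0.0314; early hazard = 0.157; 235 × 0.157 × 45/365.25 = 4.5 events.

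**Hand check of the last case.** Each arm expects 235 × 0.1711 = 40.2 events. After removing 4.5, the TEVAR group has 35.7 events in 230.5 people, a cumulative hazard of 0.168.

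- Moved to control: 44.7 events in 239.5 people, cumulative hazard 0.207. HR = 0.168 / 0.207 = 0.81.
- Excluded: control unchanged at 0.188. HR = 0.168 / 0.188 = 0.90.

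**Simulation.** Cox model from randomisation, true HR 1, 5-year risk held at 17.11%, waits uniform from zero to twice the mean, and a further 2.5% of the TEVAR arm unstented at random. Each range runs from a constant hazard to a fivefold early hazard.

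| Mean wait | Events before stent | HR, moved to control | HR, excluded |
|---|---|---|---|
| 7 days | 0.2 to 0.7 | 1.00 to 0.96 | 1.00 to 0.98 |
| 14 days | 0.3 to 1.4 | 0.98 to 0.94 | 0.99 to 0.97 |
| 30 days | 0.7 to 3.0 | 0.96 to 0.86 | 0.98 to 0.92 |
| 45 days | 1.1 to 4.5 | 0.94 to 0.81 | 0.97 to 0.89 |

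Grouping as randomised gives 0.99 to 1.01 throughout. The 45-day row lets some waits reach 90 days; capping them at 80 moves the extremes only to about 0.82 and 0.90. Withholding TEVAR because of illness is not modelled and would add to the bias.

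**If controls stented late were counted as TEVAR.** 26.5% × 78% = 20.7%, and 235 × 0.207 = about 49 people (about 44 in the simulation, because some have an event first). With no true effect:

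- late stenting unrelated to risk: HR 0.64 to 0.82;
- adding section 7.1's 8% risk of a severe event after late stenting (constant hazard, mean wait 14 or 30 days): 0.93 to 0.94;
- 8% and a doubled hazard after stenting: 1.07 to 1.08;
- 8% and a tripled hazard: 1.17 to 1.20.

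The doubling and tripling are assumptions that stand for disease progression. The sign of this component is not fixed.

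**The case against.** **ITT is primary and this is one sensitivity analysis, with detail left to the SAP.** True, and it limits the consequence. The SAP may well define major violations. But a SAP that follows the protocol's grouping rule inherits the bias; only a change to the rule removes it.

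**Participants never stented may be excluded as violations, not counted as controls.** The text does not settle this. Exclusion roughly halves the bias and leaves its direction unchanged.

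**The early risk may be low.** Participants are out of critical care and off opiates, complicated dissection is excluded, and section 7.1 puts early severe non-fatal events in the medical arm at 0%. That is a fair argument for the upper end of the range, where the hazard ratio is close to 1. It does not help those who miss TEVAR through illness. Larger distortions need a steeper early hazard than the fivefold one used here, for which the documents give no basis.

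**Late stenting in controls is not crossover.** A reader might infer that about a fifth of the control arm will be moved to TEVAR and that the whole analysis therefore favours TEVAR. The documents do not support that. Section 5.1 defines the technology as sub-acute TEVAR, sections 1.5, 2.1 and 5.2 place later repair in the control strategy, and the 2.5% crossover assumption in 7.1 makes sense only if late stents are not crossovers. Moving these controls is the less likely reading, and its effect could go either way. What stands is that 7.3(v) does not repeat the limit.

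**Conclusion.** The defect holds in a limited form. Section 7.3(v) gives the per-protocol name to an as-treated grouping. With time zero at randomisation, that grouping removes events before stenting from the TEVAR group and favours TEVAR whichever way the participants are handled. With no true effect the hazard ratio is about 0.81 to 1.00 if they are moved and 0.89 to 1.00 if they are excluded. Those ranges rest on assumed mean waits of 7 to 45 days and early hazards of 1 to 5 times the later hazard; with prompt stenting the bias is near zero.

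The direction is secure for this component only. The handling of controls stented late is an ambiguity to close, not a demonstrated bias towards TEVAR. The primary ITT analysis is unaffected. The wording should be corrected before the analysis is presented beside ITT.

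**What to change.** In section 7.3(v), and in the SAP to match:

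1. Delete the words that group participants by treatment received. Keep everyone in the randomised arm and define per-protocol by adherence to the allocated strategy.
2. State that a TEVAR-arm participant with a primary event before TEVAR, within the sub-acute window, stays in the TEVAR arm with the event counted.
3. State that, for this analysis set, later clinically indicated repair in the BMT+SURV arm is not a deviation, since sections 1.5, 2.1 and 5.2 already include it in that strategy.
4. If an effect of treatment actually received is wanted, name it as a separate analysis and use a method that respects timing: TEVAR as a time-dependent exposure, censoring at deviation with inverse-probability weights, or a randomisation-based estimate. This step is optional; items 1 to 3 are enough to cure the defect.

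The cost is one paragraph and, if item 4 is taken up, slightly more analysis. No new data should be needed: section 5.1 already has procedural details and intervention adherence recorded on the TEVAR form, and 7.3(v) already plans censoring weights for another sensitivity analysis.
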